3.1 Statistical Software

Statistical software use for analyses is the same as described in the M-SAP.

3.2 Summary Statistics

Data summaries are the same as described in the M-SAP.

Summary statistics for time-to-event endpoints will include the percentage of subjects having the event and relevant percentiles of the survival curve depending on frequency of a given event.

3.3 Precision

Precision of reported results is the same as described in the M-SAP.

³ Adverse events that occur after signing the master protocol consent form will be recorded.

⁴ Participants who continue into OLE will have a Follow-Up Safety Call (as described in the body of the RGE RSA) after their last dose of investigational product during the OLE period.

⁵ The duration of the OLE is 52 weeks.

⁶ Participants who continue into the OLE and then withdraw consent or early terminate will be asked to complete an Early Termination Visit and Follow-Up Safety Call as described in the RGE RSA.

⁷ Visit may be conducted via phone or telemedicine with remote services instead of in-person if this is needed to protect the safety of the participant due to a pandemic or other reason.

⁸ If the participant receives an in-clinic infusion within the visit window, this visit may be conducted while the participant is in clinic for their weekly infusion.

⁹ During each infusion, vital signs associated with the infusion (systolic and diastolic pressure, respiratory rate, and heart rate) are to be measured pre-infusion, 30 minutes (\pm 5 mins) after the start of infusion (SOI), 60 minutes after the start of infusion (\pm 10 mins), and 90 minutes (\pm 10 mins) after the start of infusion. If a participant requires a 90-minute infusion duration due to receiving more than 2 bags of study drug an additional vital signs measurement is to be completed approximately 30 minutes (\pm 10 mins) after the end of the 90-minute infusion.

¹⁰ The weight collected during each in clinic visit will be used to calculate the participant's dose. The participant will remain on a stable dose until the next in clinic visit (Weeks 4, 8, 16, 28, 40) when weight be collected, at which point the dose may be adjusted if the participant's weight has increased or decreased by 2 kg. Additional information on dose adjustments is included in Section 5.6 Dosing Changes of the RGE RSA.

¹¹ Drug accountability will not be done at phone visits. Compliance will be automatically calculated in the EDC.

3.4 Transformations

Data transformations are the same as described in the M-SAP.

3.5 Multiplicity Adjustments

The primary endpoint will be tested first, and key secondary endpoints will be tested next in a fixed sequence with overall family-wise error rate controlled by a closed-testing procedure as indicated in Section 6.5.1 Hierarchical Testing below. Exploratory endpoints and safety evaluations will report unadjusted p-values.

3.6 Missing Data

Handling of missing data is the same as described in the M-SAP except as indicated below. Missing baseline covariates will be mean imputed. Any transformed covariates will be transformed prior to mean imputation. Clinic-based assessments that are missing due to COVID-19 restrictions or disruptions are considered missing completely at random.

Handling of missing data depends upon the type and pattern of missing data (monotone, non-monotone, deaths), the endpoint analyzed (ALSFRS-R, SVC, HHD, etc.), the method of analysis (continuous, time to event), and the reason for missing data (related to lack of efficacy, related to tolerability, administrative reasons unrelated to lack of efficacy or tolerability, and unknown reasons). Deaths are considered a special type of missing data.

For analysis of continuous endpoints, the method described in the M-SAP for handling missing data will be followed.

For time-to-event analyses that depend on scheduled assessments, participants lacking any post-baseline assessment not due to death or disease progression will be censored at baseline and functionally omitted from the analysis. If data are missing not due to death, no imputation will be made for the primary analysis. As a sensitivity analysis, multiple imputations as described in Section 6.5.10 Placebo Multiple Imputation below will be used. All subjects who die or reach a death equivalent before reaching the pre-specified time-to-event will be considered as having the unfavorable event being analyzed at the time of death or death equivalent.

4. Study Endpoints

4.1 Efficacy Endpoints

4.1.1 Primary Efficacy Endpoint

The primary efficacy endpoint is the same as described in the M-SAP.

4.1.2 Key Secondary Efficacy Endpoints

The following key secondary efficacy endpoints will be evaluated hierarchically (see Section 6.5.1):

Combined analysis of function and survival (CAFS) using ALSFRS-R total score as the
functional measure, freedom from death and permanent assisted ventilation (PAV) as the
survival component, evaluated to the Week 24 time point, and adjusting the rank-sums for
baseline covariates of pre-baseline slope of ALSFRS-R, time since symptom onset, use of
edaravone, use of riluzole, and log-transformed serum NfL level,

- Change from baseline to Week 24 in ALS functioning as assessed using ALSFRS-R total score change from baseline,
- Change from baseline to Week 24 in respiratory function as assessed by slow vital capacity (SVC) and measured as percent predicted using Global Lung Initiative (GLI) normal values,
- Change from baseline to Week 24 in upper limb muscle strength as assessed isometrically
 using hand-held dynamometry (HHD) and grip strength and measured as average percent
 change from baseline among maneuvers with non-zero strength at baseline,
- Change from baseline to Week 24 in lower limb muscle strength as assessed isometrically
 using HHD and measured as average percent change from baseline among maneuvers with
 non-zero strength at baseline, and
- Survival defined as freedom from death and PAV from baseline to Week 24.

4.1.3 Exploratory Efficacy Endpoints

The following exploratory efficacy endpoints will be evaluated:

- Change from baseline to Week 24 in ALSFRS-R domain scores: bulbar, fine motor, gross motor, respiratory, and fine and gross motor combined,
- Change from baseline to Week 24 in combined upper and lower limb muscle strength as assessed isometrically using HHD and grip strength and measured as average percent change from baseline among muscles or muscle groups with non-zero strength at baseline,
- Time to loss of measurable strength of the first (HHD0) and second (HHD0²) muscle or muscle group with non-zero strength at baseline,
- Change from baseline to Week 24 in biofluid biomarkers of neurodegeneration, neuromuscular degeneration, and autophagy: serum creatinine, serum and cerebrospinal fluid (CSF) neurofilament light chain (NfL), and the lipid modified form of microtubule-associated proteins 1A/1B light chain 3B (LC3-II) in CSF,
- Change in patient-reported outcomes: ALSAQ-40 physical mobility, independence in activities of daily living, eating and drinking, communications, and emotional reactions domain scores and ALSAQ-40 total score, and CNS-BFS total score,
- Time to clinical events during the placebo-controlled period: first hospitalization due to a serious adverse event (SAE), first hospitalization due to an ALS-related SAE, first use of assisted ventilation, first placement of a feeding tube, first time reaching King's stage 4a or 4b, and first instance of any of the following events: hospitalization for an SAE, feeding tube placement, tracheostomy, initiation of PAV, or death,
- Survival defined as freedom from death and PAV and freedom from death alone from baseline to the last participant's last visit in the placebo-controlled period (RCT LPLV) analyzed in the ERO analysis set,
- CAFS analyses of ALSFRS-R total score and SVC as functional measures, freedom from death and PAV or from death alone as survival components, evaluated to the RCT LPLV time point, and adjusting the rank-sums for baseline covariates of pre-baseline slope of ALSFRS-R, time since symptom onset, use of edaravone, use of riluzole, and logtransformed serum NfL level analyzed in the ERO analysis set.

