		-42 to -1 Days 	-41 to 0 Day 	Day 0	Day 14 ±3	Day 28 ±7	Day 56 ±7	Day 84 ±3	Day 112 ±7	Day 140 ±3	Day 168 ±7	28 days after last dose ±3 days
Biomarker Urine Collection 	Master			X			X		X		X	
PK Blood Collection 	Regimen			X			X					
DNA Collection  (optional)	Master			X								
CSF Collection (optional)	Master			X					X 			
Concomitant Medication Review	Master	X	X	X	X	X	X	X	X	X	X	
Adverse Event Review 	Master	X	X	X	X	X	X	X	X	X	X	X
Document changes in health, medications, and infusion-related adverse events	Regimen				Weekly in conjunction with study drug administration from week 1 through week 24							
Columbia-Suicide Severity Rating Scale	Master			X		X	X		X		X	
Assignment to the Regimen	Master	X										
Randomization within the Regimen	Master		X									
Adjust Dose as Needed 	Regimen					X	X		X		X 	
Administer/Dispense Study Drug	Master			X 	Weekly IV infusion from week 1 through week 24						X 	
Drug Accountability/Compliance	Master				Weekly in conjunction with study drug administration from week 1 through week 24 						X	
Exit Questionnaire	Master										X	
Vital Status Determination 	Master										X	

- 1 Master Protocol Screening procedures must be completed within 42 days to 1 day prior to the Baseline Visit. The Regimen-Specific Screening Visit and Baseline Visit should be combined, if possible.
- 2 During the Master Protocol Screening Visit, participants will be consented via the Platform Trial informed consent form (ICF). After a participant is randomized to a regimen, participants will be consented a second time via the regimen-specific ICF.
- 3 At the Regimen Specific Screening Visit, participants will have regimen-specific eligibility criteria assessed.
- 4 Vital signs include weight, systolic and diastolic pressure, respiratory rate, heart rate and temperature. Height measured at Master Protocol Screening Visit only. If an infusion will occur at the completion of the visit, vital signs should be collected within 30 minutes of the start of infusion to serve as the pre-infusion vital signs collection.

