- 5 During each infusion, vital signs associated with the infusion (systolic and diastolic pressure, respiratory rate, and heart rate) are to be measured pre-infusion, 30 minutes ( $\pm 5$  mins) after the start of infusion (SOI), 60 minutes after the start of infusion ( $\pm 10$  mins), and 90 minutes ( $\pm 10$  mins) after the start of infusion. If a participant requires a 90-minute infusion duration due to receiving more than 2 bags of study drug an additional vital signs measurement is to be completed approximately 30 minutes ( $\pm 10$  mins) after the end of the 90-minute infusion.
- 6 Clinical safety labs include hematology (CBC with differential), complete chemistry panel, thyroid function and urinalysis. Hb A1C will be included in labs at baseline, week 16 and week 24. Serum pregnancy testing will occur in women of child-bearing potential at the Master Protocol Screening Visit and as necessary during the study. Pregnancy testing is only repeated as applicable if there is a concern for pregnancy.
- 7 Adverse events that occur after signing the master protocol consent form will be recorded.
- 8 The DNA sample can be collected after the Baseline Visit if a baseline sample is not obtained or the sample is not usable.
- 9 Administer first dose of study drug only after Baseline Visit procedures are completed.
- 10 Participants will only have a Follow-Up Safety Call at this time if they *do not* continue on in the OLE. Participants who continue into OLE will have a Follow-Up Safety Call after their last dose of investigational product during the OLE period.
- 11 Vital status, defined as a determination of date of death or death equivalent or date last known alive, will be determined for each randomized participant at the end of the placebo-controlled portion of their follow-up (generally the Week 24 visit, as indicated). If at that time the participant is alive, his or her vital status should be determined again at the time of the last patient last visit (LPLV) of the placebo-controlled portion of a given regimen. We may also ascertain vital status at later time points by using publicly available data sources as described in section 8.15 of the Master Protocol.
- 12 If the CSF collection is unable to be performed for logistical reasons, such as scheduling, at the Week 16 Visit, it may be performed at the Week 24 Visit.

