#### Exploratory Efficacy Endpoints:

- Changes in the biofluid biomarkers of neurodegeneration specified in the SOA.
- Changes in the patient reported outcomes specified in the SOA.

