### **8.1 CSF Biomarker Collection**

The CSF for neurofilament light chain concentration and microtubule-associated protein 1A/-light chain 3 (LC3-II) will be obtained from participants who consent to lumbar puncture. Four cryovials containing 0.25 mL of CSF (for a total of 1.0 mL) will be provided from the Baseline and Week 16 Visits for analysis. Details regarding sample collection preparation and shipment will be provided in laboratory manual.

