This Regimen-specific Statistical Analysis Plan (R-SAP) for the trehalose regimen (RGE) specifies any modification from the default outcome measures, analysis samples, and planned analyses for the placebo-controlled period of the HEALEY ALS Platform Trial as specified in the Master SAP (M-SAP) and adds analyses specific to the open-label extension (OLE) period. The M-SAP and this R-SAP supplement the Master Protocol, the "ALS Master Protocol Recommended Statistical Analysis, Design and Simulation Report" (Appendix 1 to the Master Protocol), and the RGE Regimen-specific Appendix (RSA). Please refer to the Master Protocol and the RGE RSA for details on the rationale for the study design, eligibility criteria, conduct of the trial, clinical assessments and schedule of assessments, definitions and reporting of adverse events, data management conventions, and regulatory oversight and compliance procedures. The "ALS Master Protocol Recommended Statistical Analysis, Design and Simulation Report" (MPRDR) and any regimen-specific deviations described in the RGE RSA and this R-SAP are authoritative in defining the primary and interim analyses. In case of discrepancies between the RGE RSA and this R-SAP concerning use of shared placebos, this R-SAP is authoritative. In case of discrepancies between either SAP and the Master Protocol and the RGE RSA concerning matters of analysis other than the primary and interim analyses and use of shared placebos, the M-SAP and this R-SAP are authoritative. In case of discrepancies between the M-SAP and this R-SAP, this R-SAP is authoritative. On all matters not related to analysis, the Master Protocol and the RGE RSA are authoritative. The following table describes relationships among the relevant documents in adjudicating possible discrepancies with higher numbers indicating greater authority.

	Master	RGE			RGE
Issues potentially requiring adjudication	Protocol	RSA	MPRDR	M-SAP	R-SAP
Use of shared placebos	1	4	2	3	5
Primary and interim analysis specifications not related to use of shared placebo	1	5	4	2	3
Statistical analysis specifications not related to use of shared placebo or primary and interim analyses	1	3	2	4	5
All matters not related to statistical analysis	4	5	1	2	3

2. Study Design

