- ⁷ Adverse events that occur after signing the Master Protocol consent form will be recorded.
- ⁸ The DNA sample can be collected after the Baseline Visit if a baseline sample is not obtained or the sample is not usable.
- ⁹ Administer first dose of study drug only after Baseline Visit procedures are completed.
- ¹⁰ Participants will only have a Follow-Up Safety Call at this time if they do not continue into the OLE. Participants who continue into OLE will have a Follow-Up Safety Call after their last dose of investigational product during the OLE period.
- ¹¹ Vital status, defined as a determination of date of death or death equivalent or date last known alive, will be determined for each randomized participant at the end of the placebo-controlled portion of their follow-up (generally the Week 24 visit, as indicated). If at that time the participant is alive, his or her vital status should be determined again at the time of the last patient last visit (LPLV) of the placebo-controlled portion of a given regimen. We may also ascertain vital status at later time points by using publicly available data sources as described in section 8.15 of the Master Protocol.
- ¹² If the CSF collection is unable to be performed for logistical reasons, such as scheduling, at the Week 16 Visit, it may be performed at the Week 24 Visit.
- ¹³ Visit may be conducted via phone or telemedicine with remote services instead of in-person if this is needed to protect the safety of the participant due to a pandemic or other reason.
- ¹⁴ If required due to pandemic-related restrictions, Forced Vital Capacity (FVC) performed by a Pulmonary Function Laboratory evaluator or with a study-approved home spirometer, or sustained phonation using a study approved method may be used for eligibility (Master Protocol Screening ONLY).
- ¹⁵ Master Protocol Screening and Regimen Specific Screening visit windows are relative to Baseline (Day 0).
- 16 Participants completing the PK collection will have blood collected for PK analysis at Baseline (Day 0) and Week 8 (Day 56) at the following time points: pre-dose and 1 hour \pm 5 minutes, 2 hours \pm 5 minutes, and 4 hours \pm 5 minutes post start of infusion. At each time point, 4 mL of blood will be collected.
- ¹⁷ All urine samples must be collected prior to IP administration.
- ¹⁹ Dose is adjusted only for those participants continuing into the OLE.

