5.11 Pharmacodynamic Biomarkers

CSF LC3-II levels in samples collected at Baseline and Weeks 16 or 24 will be assayed. The method of analysis of CSF LC3-II will be specified once known. Levels of CSF LC3-II that are reported to be below the limit of quantitation will be imputed at the limit of quantitation. Levels of CSF LC3-II will be log-transformed in all analyses.

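### CSF LC3-II and NfL are defined as change to Week 24, but the one follow-up CSF draw is scheduled at Week 16, and no matching contrast is named for LC3-II

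*SAP*

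**What the plan says.** **Endpoint.** SAP Section 4.1.3 sets the exploratory biomarker endpoint as "Change from baseline to Week 24 in biofluid biomarkers of neurodegeneration, neuromuscular degeneration, and autophagy". The list under it includes CSF NfL and CSF LC3-II alongside the serum markers.

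**Sampling.** The placebo-controlled schedules in the Protocol and in SAP Section 2.9 mark the optional CSF row at Baseline and Week 16 only. Footnote 12 in both documents provides that, if logistics prevent collection "at the Week 16 Visit, it may be performed at the Week 24 Visit". Protocol Section 8.1 says that the CSF aliquots "will be provided from the Baseline and Week 16 Visits for analysis". SAP Section 5.11 states: "CSF LC3-II levels in samples collected at Baseline and Weeks 16 or 24 will be assayed".

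**Precedence.** Protocol Section 2.1 words the endpoint as "Changes in the biofluid biomarkers of neurodegeneration specified in the SOA" and names no week. SAP Section 1 provides that, for discrepancies "concerning matters of analysis other than the primary and interim analyses and use of shared placebos, the M-SAP and this R-SAP are authoritative", and it ranks this regimen SAP above the Master SAP.

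**Analysis.** SAP Section 6.5.14 summarises CSF LC3-II by arm and visit and refers the treatment effect to the model in Section 6.5.3. The primary estimate there is the between-arm difference in change to the Week 24 Visit. Its contrast code is written for an endpoint measured every 8 weeks. Section 6.5.3 lists serum NfL among its endpoints, but neither CSF NfL nor LC3-II.

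**The concern.** A participant who consents to lumbar puncture is planned to give one follow-up sample, normally at Week 16. The endpoint definition and the only stated model estimate both look at Week 24, where most participants will have no CSF value. The supplied documents name no Week 16 contrast, no combined Week 16/24 contrast, and no rule assigning the single draw to one analysis visit.

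CSF LC3-II is the plan's autophagy marker, and autophagy activation is one of the proposed mechanisms of trehalose. If the text is followed literally, the stated treatment-effect estimate for that marker either rests on the few rescheduled draws or fails. SAP Section 7.2 says that analyses failing through small samples or non-convergence are dropped with a comment, not reworked. If the text is not followed literally, the choice between Week 16, Week 24 and a pooled estimate falls to the analyst and is not pre-specified.

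**Working it through.** The plan gives no sample size or precision for the CSF endpoints, so there is no figure to reproduce. The check has two parts.

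**1. Time points side by side**

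| Place | Follow-up time for CSF |
|---|---|
| SAP 4.1.3 (endpoint) | Week 24 |
| SAP 6.5.3, reached from 6.5.14 (primary estimate) | Week 24 |
| Protocol and SAP schedules | Week 16 |
| Footnote 12, both documents | Week 16; Week 24 only as logistical substitute |
| Protocol 8.1 | Week 16 |
| SAP 5.11 (samples assayed) | Week 16 or 24 |

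The statements of what is estimated say Week 24. The statements of when CSF is drawn make Week 16 the default. The printed contrast in Section 6.5.3, `trtrnd*visit 1 0 0 -1 -1 0 0 1`, has eight coefficients, for two arms and four visits. CSF has at most three visit levels (six cells), so the code does not fit.

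**2. What the Week 24 contrast costs (illustration)**

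Assumptions, none of which the documents supply:
- Each CSF participant has a baseline and exactly one follow-up sample.
- A fraction f is drawn at Week 24 and 1 − f at Week 16, with the same f in both arms.
- Variance is equal at all visits (set to 1), with baseline to follow-up correlation rho.
- The covariance is known, treatment effects are visit-specific, and there are no covariates.

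In an arm of n participants, generalised least squares gives:
- Week 24 change: variance = [(1 − rho²)/f + (1 − rho)²] / n. The first term comes from the nf Week 24 samples after adjustment for baseline; the second comes from the baseline mean of all n participants.
- All follow-up samples coded as one visit: variance = 2(1 − rho)/n.

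Dividing and taking the square root, n cancels:
- Week 24 SE ratio = sqrt{[(1 + rho)/f + 1 − rho]/2}
- Week 16 SE ratio = sqrt{[(1 + rho)/(1 − f) + 1 − rho]/2}

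Worked extremes for Week 24:
- f = 0.05, rho = 0.9: sqrt[(38 + 0.1)/2] = sqrt(19.05) = 4.365
- f = 0.30, rho = 0.5: sqrt[(5 + 0.5)/2] = sqrt(2.75) = 1.66

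| f | Week 24 ratio, rho 0.5 / 0.7 / 0.9 | Week 16 ratio, rho 0.5 / 0.7 / 0.9 |
|---|---|---|
| 0 | not estimable | 1 |
| 0.05 | 3.91 / 4.14 / 4.37 | 1.02 / 1.02 / 1.02 |
| 0.10 | 2.78 / 2.94 / 3.09 | 1.04 / 1.05 / 1.05 |
| 0.20 | 2.00 / 2.10 / 2.19 | 1.09 / 1.10 / 1.11 |
| 0.30 | 1.66 / 1.73 / 1.79 | 1.15 / 1.17 / 1.19 |

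The closed forms were confirmed numerically with 60 active and 20 placebo participants.

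**Do Week 16 samples help the Week 24 contrast?** They enter the fit through the visit and treatment-by-visit terms. Because those terms are saturated and nobody is planned to have both draws, a Week 16 value informs only the Week 16 mean. Numerically, the largest weight on any Week 16 value in the Week 24 contrast was below 1e-15. This held without covariates (f = 0.10, 0.20, 0.30) and with five visit-crossed covariates (f = 0.20, 0.30; rho 0.5 and 0.9). Only the baselines of those participants contribute.

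For the same reason, the Week 16/Week 24 element of the unstructured covariance matrix in Section 6.5.3 is not identified.

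**The case against.** - **Section 1 settles conflicts between documents, and this one lies partly inside the SAP.** Sections 2.9 and 5.11 have the same rank as 4.1.3. That is fair, but Sections 2.9 and 5.11 say when CSF is drawn and which samples are assayed. For what is estimated, the SAP offers only Week 24.
- **Section 6.5.14 partly works as written.** The by-visit summaries will show Week 16 change by arm, and the correlations with concurrent ALSFRS-R and SVC change can be computed. This stands. It limits the problem to the model-based treatment effect, which those outputs do not replace.
- **Section 6.5.14 cites the model, not its primary contrast, so an analyst could report Week 16 from the same fit.** The fit could give that contrast, but nothing names it, and the only estimate Section 6.5.3 designates is Week 24.
- **The Master SAP, which was not supplied, may hold a visit-assignment rule.** It should be checked, above all for CSF NfL. Where it conflicts with the Week 24 wording, Section 1 puts this SAP first.
- **The ratios rest on assumed inputs.** Correct. If half the draws were rescheduled, the Week 24 ratio would fall to 1.3–1.4. The calculation also treats the covariance as known, so it does not show any convergence trouble from the unidentified element. The mismatch in the text does not depend on these figures.
- **Pooling two follow-up times is a choice, and a plain Week 16 contrast costs little.** Also true; either would repair the plan if named in advance.

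**Conclusion.** The concern holds. Both CSF endpoints are defined at a week when CSF is not routinely drawn. For LC3-II, the stated treatment-effect estimate depends on rescheduled draws and cannot be estimated if there are none. For CSF NfL the time-point mismatch is the same, but whether any model is specified has to be confirmed in the Master SAP.

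Under the assumed 5–30% rescheduling and correlations of 0.5–0.9, the loss is a standard error about 1.7–4.4 times larger than with one combined follow-up visit. With equal rescheduling in both arms, this does not depend on how many participants consent to lumbar puncture. Confidence in the textual finding is high; the size is an illustration only. The endpoints are exploratory and the samples optional, and the primary analysis, testing hierarchy and safety analyses are untouched, so this is a low-severity point that could be corrected.

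**What to change.** 1. In SAP Sections 4.1.3 and 6.5.14, restate CSF NfL and CSF LC3-II as change in log concentration from baseline to the single follow-up sample (Week 16, or Week 24 if rescheduled), treated as one post-baseline visit. This agrees with Section 5.11 and removes the unidentified covariance element.
2. Name the matching contrast of the Section 6.5.3 model as the treatment-effect estimate. With two visits and the active group sorted last, it is `trtrnd*visit 1 -1 -1 1`.
3. Add a sensitivity analysis restricted to Week 16 samples.
4. Confirm in the Master SAP which model applies to CSF NfL, and state it in this SAP.

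The cost is SAP wording only; sampling does not change. The drawback is that the endpoint mixes two follow-up times for rescheduled participants, and the Week 16-only analysis will show whether that matters.
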